11.1 Procedures for Recording and Reporting CIP Deviations

The process for recording deviations for the clinical investigation plan, for reporting of the deviations, development of Corrective and Preventative Actions (CAPA) and analysis of deviations shall be carried out in accordance with International Conference on Harmonisation Good Clinical Practice (ICH GCP) and as per ISO14155 requirements

CE-GAX001-01

V4.0

CR: 144

12 PRODUCT ACCOUNTABILITY

Prior to the study commencement date, the product will be shipped from Hidramed Solutions Galway and bonded stock will be shipped to and stored at the Hermitage Clinic, Lucan, Dublin.

3 garments will be supplied to subjects.

A 3 week supply of dressings will be provided to subjects.

Device packaging will be labelled "For Clinical Investigation Use Only" and will display the following information:

Packet contents

Part Number, Batch Number and Lot Number

CE-GAX001-01

V4.0

CR: 144

13 STATEMENTS OF COMPLIANCE

13.1 Statement of Compliance: ISO 14155 and National Regulations

The study will be carried out in accordance with ISO 14155

The protocol, informed consent form(s), recruitment materials, and all subject materials will be submitted to the Research Ethics Committee (REC) for review and approval. Approval of both the protocol and the consent form must be obtained before any subject is enrolled. Any amendment to the protocol will require review and approval by the REC before the changes are implemented to the study. In addition, all changes to the consent form will be REC-approved; a determination will be made regarding whether a new consent needs to be obtained from subjects who provided consent, using a previously approved consent form.

The Principal Investigator will assure that no deviation from, or changes to the protocol will take place without prior agreement from the sponsor, funding agency and documented approval from the REC except where necessary to eliminate an immediate hazard(s) to the trial subjects. All personnel involved in the conduct of this study have completed ICH GCP and relevant training. The investigation will be performed to the standards set out in the ISO 14155 standard.

13.2 Statement Regarding Ethical Approval

The Study shall not commence until written approval/favourable opinion from the Ethics Committee.

13.3 Statement of Insurance Cover

The sponsor has insurance in place for the clinical investigation.

CE-GAX001-01

V4.0

CR: 144

14 INFORMED CONSENT PROCESS

14.1 General Informed Consent

All documents below will be provided in English only.

Informed consent will be obtained in writing by the PI or a delegate from the subject prior to any procedures specific to the clinical investigation being applied to the subject.

The Subject Information Leaflet (SIL) and Informed Consent Form (ICF)

SIL and ICF will be prepared in accordance with ISO 14155 Good Clinical Practice

Subjects will be invited to participate in the study and will be given the SIL to review.

Subjects will be given adequate time to read the SIL and ICF and ask questions before signing the consent form.

14.2 Informed Consent in Special Circumstances

Informed consent will not be sought from infants, children, juveniles, seriously ill, mentally incapacitated or unconscious subjects.

14.3 Subjects unable to read or write:

Informed consent will not be sought from subjects unable to read or write.

CE-GAX001-01

V4.0

CR: 144

15 ADVERSE EVENTS, ADVERSE DEVICE EVENTS AND DEVICE DEFICIENCIES

15.1 Definition: Adverse Event (AE)

An Adverse Event (AE) is defined as any untoward medical occurrence, unintended disease or injury, or any untoward clinical signs (including abnormal laboratory findings) in subjects, users or other persons, whether or not related to the investigational medical device.

This includes:

- Events related to the investigational medical device
- Events related to procedures involved (any procedure in the clinical investigation plan)
- For users and other persons, this definition is restricted to events related to the investigational medical device.

15.2 Definition: Adverse Device Effect (ADE)

An Adverse Device Effect (ADE) is defined as an adverse event related to the use of an investigational medical device resulting from insufficient or inadequate instructions for use, deployment, implantation, installation, operation, any malfunction, user error, or intentional misuse of the investigational medical device

Subjects will be fully trained on how to use the device and be provided with instructions for use. Subjects can contact research nurse at any time if unsure, and can send daily comments to the researcher through daily check ins.

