2.4 Contraindications and Warnings

A full list of contraindications and warnings are provided in the IFU supplied with the device.

Contraindications: Known allergies to materials specified

Warnings: Do not use if you have known allergies to materials specified.

Warnings

- 1. The garment is not a wound dressing wound(s) should be fully covered by dressing(s).
- 2. If any unexpected discomfort or wound irritation occurs, please consult your doctor or nurse.
- 3. Do not use, if you have a known allergy or sensitivity to materials listed.

CE-GAX001-01

V4.0

CR: 144

Potential side effects: Dermatitis, infection and skin irritation or skin abrasion.

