4 RISKS AND BENEFITS

4.1.1 Risk Analysis

- Hidradenitis Suppurativa wounds can sometimes be colonised by non-pathogenic bacteria, and may appear to be infected. This is not a true infection. However, subjects will examined by research nurse to assess the wound and will be asked to record their temperature during the study to monitor for signs of infection. There will be a registered nurse overseeing all subject interactions and demonstrations to ensure the safety of subjects
- Garment could cause discomfort to the subject. In the case of any discomfort the subject is requested to remove the wound care product
- There is also a minor concern re allergies to certain materials and this will be included in the PIL and will be an exclusion criteria

Risk assessment for Hidramed vs Standard Adhesive dressing.

Risk level and likelihood rated 1-5, 1 being the lowest and 5 being the highest.

Hidrawear AX Garment

Risk	Cause	Level of Risk	Likelihood of Risk	Control
Skin Irritation	Allergic to garment	1	1	Discontinue use immediately
Unnecessary Pain	Difficult dressing site			Use product as instructed exactly.
				Discontinue use immediately
Subject distress and embarrassment	Dressing leaking or falling off.	1	1	Use product as instructed exactly
Physical contamination of wound	Thread or fibres from product retained in wound	1	1	Selected bonded fabric that does not fray/produce fibres.
				Users instructed to carry out daily visual inspection of wound.
				Discontinue use immediately

CE-GAX001-01

V4.0

CR: 144

Dressing Supplied During Study

Risk	Cause	Level of Risk	Likelihood of Risk	Control
Skin Irritation	Allergic to dressings	1	1	Discontinue use immediately
Localised infection	Misuse of dressings	3	1	Follow user instructions exactly. Discontinue use immediately
Septicemia	Misuse of dressings	5	1	Follow user instructions exactly. Discontinue use immediately
				Monitor temperature twice daily during pilot period.
Subject distress and embarrassment	Dressing leaking or falling off.	1	1	Use product as instructed exactly

Standard Adhesive Dressing

Risk	Cause	Level of Risk	Likelihood of risk	Control
Skin Irritation	Allergic to or reaction to adhesive in dressing	1	3	Discontinue Use immediately
Localised infection	Misuse of dressings	3	3	N/A user instructions do not specify
Septicemia	Misuse of dressings	5	1	N/A user instructions do not specify
Unnecessary pain	Difficult dressing site, Adhesive damage to skin	5	4	N/A

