4.3 Adverse Device Effects

Materials selected are designed for contact with the skin and all use of adhesives on the skin have been removed so the likelihood of adverse effects due to using the device is low. However, there is a slight possibility of skin irritation, infection and pain due to misuse of the device. See table in section 4.1.1

In all instances of adverse effects, subjects must cease using the device immediately and make contact with research nurse for further instruction.

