15.3 Definition: Device Deficiency

An Adverse Device Effect (ADE) is defined as an adverse event related to the use of an investigational medical device resulting from insufficient or inadequate instructions for use, deployment, implantation, installation, operation, any malfunction, user error, or intentional misuse of the investigational medical device

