15.5 Definition: Unanticipated Serious Device Effect (USADE)

A Serious Adverse Device Event (SADE) is an adverse device effect that has resulted in any of the consequences characteristic of a serious adverse event.

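### Section 15.2 ties an adverse device effect to a list of faults, so a skin reaction to a sound garment worn as instructed is an adverse event but not a device effect

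*Combined protocol and SAP*

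**What the plan says.** Section 15.1 defines an adverse event broadly, whatever its relation to the device, and names "Events related to the investigational medical device" among the events included.

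Section 15.2 narrows this for ADEs. The event must be one "related to the use of an investigational medical device resulting from insufficient or inadequate instructions for use" or from another cause on the list, which in full reads "resulting from insufficient or inadequate instructions for use, deployment, implantation, installation, operation, any malfunction, user error, or intentional misuse of the investigational medical device".

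Section 15.3 is headed as the definition of a device deficiency but repeats the ADE sentence: an ADE "is defined as an adverse event related to the use of an investigational medical device resulting from insufficient or inadequate instructions for use", and so on to the same end.

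Section 15.5 says that a SADE "is an adverse device effect that has resulted in any of the consequences characteristic of a serious adverse event". An event must therefore be an ADE before it can be a SADE.

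Elsewhere the protocol describes what the device may do to the skin:

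- Section 2.4: "Potential side effects: Dermatitis, infection and skin irritation or skin abrasion", with no mention of misuse.
- Section 4.1.1, garment table: the cause given for skin irritation is "Allergic to garment".
- Section 4.3, headed as adverse device effects: "there is a slight possibility of skin irritation, infection and pain due to misuse of the device". It then refers the reader to the table in 4.1.1.

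**The concern.** The phrase *resulting from* in 15.2 sets a required cause. Being related to the device is not enough: the event must also come from a failure of instructions, a malfunction, a user error or deliberate misuse. A contact reaction to a garment that is intact and correctly worn has none of these causes, although it comes from the device.

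Section 3.4 says that the pilot evaluates safety, and 7.1 lists adverse events among its purposes. For a garment worn against diseased skin, readers will want to know which events the device caused. If the label for device-caused events leaves out reactions in correct use, a tally made with that label understates them. Two assessors could also label the same rash differently, one by relatedness and the other by the 15.2 list. Section 16.1 makes unanticipated device effects a ground for suspending or ending the study, so the label may matter beyond a results table.

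**Working it through.** The documents give no expected ADE or SADE rate, so there is no figure to reproduce. The check applies the definitions to the events that the protocol itself foresees.

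**Step 1. One event taken through section 15.** Take an allergic or irritant reaction to an undamaged garment, in a trained subject who followed the instructions.

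| Section | Test | Result |
|---|---|---|
| 15.1 | Untoward medical occurrence, related to the device or not | Adverse event |
| 15.2 | Related to use of the device | Met |
| 15.2 | Results from inadequate instructions, malfunction, user error or intentional misuse | Not met, so not an ADE |
| 15.3 | Same sentence as 15.2 | Adds no wider category |
| 15.4 | If serious, whether or not associated with the device | SAE |
| 15.5 | Must first be an ADE | Not a SADE |

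**Step 2. Is the list closed?** No word such as *including* makes it illustrative. The one doubtful item is *operation*. It most naturally completes the phrase about instructions, along with deployment, implantation and installation. If it is read as a cause in its own right, events in normal operation could qualify. The text does not settle this.

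**Step 3. The four garment rows of 4.1.1 against the 15.2 list.**

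| Hazard | Stated cause | On the 15.2 list? |
|---|---|---|
| Skin irritation | Allergy to the garment | No |
| Unnecessary pain | Difficult dressing site | Arguable: the cause is anatomical, but a listed control is to follow the instructions exactly |
| Distress and embarrassment | Dressing leaks or falls off | Can be read as malfunction or user error |
| Physical contamination of the wound | Fibres from the product left in the wound | Can be read as malfunction |

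So at least 1 of the 4 rows is clearly outside the list.

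**Step 4. Consistency with the rest of the protocol.** Section 2.4 lists dermatitis, irritation and abrasion without tying them to misuse. Section 4.3 ties irritation, infection and pain to misuse, then points to a table in which the cause of garment irritation is allergy. Sections 4.3 and 15.2 thus share the narrow view, and 2.4 and 4.1.1 do not.

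**Step 5. What depends on the label.** The endpoints in 6.1.3 and the statistical section 7 contain no ADE or SADE endpoint, table or rate. The visible use of the label is the device-effect criterion in 16.1. That criterion concerns unanticipated effects, so a reaction already foreseen in 2.4 would not obviously trigger it. An unforeseen reaction in correct use might, and 15.2 puts in doubt whether it is a device effect at all.

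**The case against.** The strongest reply is that nothing is lost. Section 15.1 expressly includes device-related events, 15.4 covers serious events regardless of association, and 15.6 has all adverse events captured. The safety aims in 3.4 and 7.1 can be met from adverse event data. In 16.1, unanticipated adverse events and other clinical reasons are separate grounds for suspension. All of this stands, and it limits the point to classification.

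Practice may also be better than the wording. In 4.6 the research nurse judges whether a pyrexia is device related, with no test of fault or misuse. Reporting follows a sponsor procedure and a vigilance guideline, under a commitment to ISO 14155. The contents of those sources are not in the documents, so how a reaction would be labelled in practice cannot be known. That is a reason not to claim that misclassification will happen. It does not mend the definition.

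A reader might infer more than the text supports:

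- *That the plan's ADE rate is biased.* The plan promises no such rate, and any numerical illustration would need an invented event count.
- *That the definition leaves out the reactions most likely to come from the garment.* Section 4.1.1 rates garment skin irritation at likelihood 1 on a scale of 1 to 5, and 4.3 attributes reactions to misuse, which 15.2 covers. Known allergy is also a contraindication (2.4) and an exclusion (6.3.3). For allergy, that leaves sensitivity not known at enrolment.
- *That half the garment hazards fall outside the list.* That count needs the difficult-site row, which is arguable.

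**Conclusion.** The point holds as a defect of definition. As 15.2 is most naturally read, a device-caused reaction in correct use is not an ADE and, if serious, not a SADE. This conflicts with 2.4 and with the allergy row of 4.1.1, and no visible passage widens the definition.

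The size is limited. No event goes unrecorded, and no endpoint, rate or count in the plan changes. What is affected is any tally made with these definitions and, possibly, the device-effect criterion in 16.1. Severity is minor to moderate.

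The conclusion rests on reading *operation* as part of the phrase about instructions, and on the sponsor procedure and external guidance not overriding 15.2, which cannot be checked here. If *operation* is a separate cause, the text is ambiguous rather than plainly too narrow, and it still needs correction.

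**What to change.** 1. In 15.2, replace *resulting from* with *including any event resulting from*. Every adverse event related to use of the device is then an ADE, and the listed causes become examples. Section 15.5 follows without further change.
2. In 15.3, remove the repeated ADE sentence and put a definition of device deficiency in its place. If only 15.2 were changed, the protocol would hold two conflicting ADE definitions.
3. Reconcile 4.3 with 2.4 and 4.1.1, so that the protocol gives one account of whether skin reactions are expected only with misuse.

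The cost is a short wording amendment, with the ethics review that section 10 requires. It changes no visit, procedure, endpoint or sample size. The downside for the sponsor is that the number of events classed as device effects may be slightly higher.

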15.3 Definition: Device Deficiency

An Adverse Device Effect (ADE) is defined as an adverse event related to the use of an investigational medical device resulting from insufficient or inadequate instructions for use, deployment, implantation, installation, operation, any malfunction, user error, or intentional misuse of the investigational medical device

15.4 Serious Adverse Event

A Serious Adverse Event (SAE) is any event (whether or not associated with the investigational device) that:

- Results in death
- Leads to serious deterioration in the health of the subject, that either resulted in
- Life threatening illness or injury, or
- Permanent impairment of a body structure or a body function, or
- In-subject or prolonged hospitalization, or
- Medical or surgical intervention to prevent life threatening illness or injury or permanent impairment to a body structure or body function.
- Leads to foetal distress, foetal death or a congenital abnormality or birth defect

CE-GAX001-01

V4.0

CR: 144

This includes device deficiencies that might have led to a serious adverse event if a) suitable action had not been taken or b) intervention had not been made or, c) if the circumstances had been less fortunate. These are handled under the SAE reporting system.

Planned hospitalisation for a pre-existing condition, without serious deterioration in health, is not considered a serious adverse event.

Subjects who experience and adverse will be released to their primary care provider/GP and excluded from the study.

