6.1.3 Primary and Secondary Endpoints

Primary Endpoint

• The change in the ease of use at week 3 compared to Day 0

Secondary Endpoints - Subject Assessment

- Ease of use W2 vs W1
- Comfort measured on a 10 point scale D21 vs D0
- Pain measured on a 10 point scale D21 vs D0
- Time measured on a 10 point scale D21 vs D0
- Dressing retention confidence measured on a 10 point scale D21 vs D0

Secondary Endpoints – Nurse Assessment

- Necessity to stretch/contort the body to apply dressing
- Did subject need assistance
- Could dressing be applied without raising arms over head
- Additional equipment used- mirror, scissors etc.

Outcome selection rationale:

- Assessment of ease of use as primary outcome was selected as most users have voiced frustration
- Comfort was selected as we wish to learn if Hidrawear AX is comfortable to use.
- Dressing retention confidence was selected as user have voiced frustration
- Dressing related pain was selected as HidraWear AX may reduce unnecessary patient distress due to dressing/adhesive related pain
- Time was selected as regular wound dressing changes are time consuming (6)

CE-GAX001-01

V4.0

CR: 144

DLQI was selected as it a validated tool that has been commonly used for assessment of quality of life for HS subjects. will assess if Hidrawear AX is better than the current products used by HS subjects.

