6.1.4 Methodology

Before the study commences on site, a survey will be shared into select closed patient groups online, to capture the patient experience of living with Hidradenitis Suppurativa (HS) in terms of self-managing wound care and the impact that HS wound care has on patients' day to day life, physically, financially and emotionally.

A secure and confidential survey tool (Typeform) will be used. This is governed under EU data legislation and encrypted to ensure privacy. The survey will not collect any identifying information and is a precursor to the HidraWear AX Pilot Study.

Day 0

Subjects will visit trial site or have a home visit from research nurse.

Following consent and enrolment, Subjects will be asked to demonstrate or explain their usual method of dressing their wound using their usual wound dressing products.

Subjects will assess this activity based on ease of use, comfort, experienced pain, confidence in dressing retention and time, using a 10 point visual analogue scale. (see appendix 2)

The subjects will complete a Dermatology Quality of Life Index Survey. (see appendix 5)

The research nurse will assess the activity based on whether the subject needs assistance, uses additional equipment, contorts or stretches their body, can dress the wound without raising their arms above their head. (See appendix 4)

Day 1-21

Daily Check in with Subjects:

Each day, at 1pm, subjects will receive an email requesting them to check in with the researcher by answering 3 questions.

- 1. What is your temperature?
- 2. How many dressings did you use in the last 24 hours?
- 3. Any comments?

This check in should take less than 5 minutes to complete.

Subjects will be required to respond by 5pm each evening. If subject has not responded by 5pm, a reminder text message will be sent to them.

If subject does not respond within 24 hours, the research nurse will call the subject to check in and take answers over the phone.

CE-GAX001-01

V4.0

CR: 144

Weekly Check in with Subjects:

On day 7 and 14 subjects will be asked to complete the Dermatology Quality of life survey and questions on Ease of use, comfort, pain and confidence, at home. A link to the surveys will be emailed to them at 1pm in the afternoon with their daily check in.

Subjects will be required to respond by 5pm each evening. If subject has not responded by 5pm, a reminder text message will be sent to them.

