If subject does not respond within 24 hours, the research nurse will call the subject to check in and take answers over the phone.

Day 21

Subjects will return to site or be visited by research nurse for review.

Subjects will be asked to demonstrate how they dress their wound using HidraWear AX.

Subjects will assess this activity based on ease of use, comfort, experienced pain, confidence in dressing retention and time, using a 10 point visual analogue scale. (see appendix 3)

The subjects will complete a Dermatology Quality of Life Index Survey. (see appendix 5)

The research nurse will assess the activity based on whether the subject needs assistance, uses additional equipment, contorts or stretches their body, can dress the wound without raising their arms above their head. (See appendix 4)

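### Subjects who stop HidraWear AX for an adverse effect can drop out of the Day 21 versus Day 0 comparison, which can favour the device

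*Combined protocol and SAP*

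**What the plan says.** **Stopping the device.** Section 4.3 states that "there is a slight possibility of skin irritation, infection and pain due to misuse of the device. See table in section 4.1.1". For any adverse effect it then requires that "subjects must cease using the device immediately and make contact with research nurse for further instruction".

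**Leaving the study.** The last line of section 15.4 reads: "Subjects who experience and adverse will be released to their primary care provider/GP and excluded from the study". The noun after the adjective is missing, and the line closes the section on serious adverse events.

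**Replacement.** Section 6.3.6 sets up a waiting list for drop-outs and excluded subjects. Enrolment from it needs the principal investigator's approval.

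**What the endpoint needs.** The primary endpoint in section 6.1.3 is "The change in the ease of use at week 3 compared to Day 0". On Day 21, section 6.1.4 says: "Subjects will be asked to demonstrate how they dress their wound using HidraWear AX". The rating follows that demonstration, and the one Day 21 form (Appendix 4) carries ease of use, comfort and pain with HidraWear AX. On Days 7 and 14 subjects also answer "questions on Ease of use, comfort, pain and confidence, at home".

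**What is not stated.** Section 7 gives no analysis set, no rule for a missing Day 21 rating and no handling of replaced subjects. Section 16.2 keeps a Day 21 nurse visit, but under its rules for suspension of the whole investigation. No such rule is stated for one excluded subject.

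**The concern.** The subjects whom these rules can remove are those with irritation, infection or pain on the garment. Their comfort and pain ratings are plausibly worse than average, and their ease-of-use ratings may be. If they give no Day 21 rating, the remaining mean change looks better than the mean for everyone who was given the device. The study is single-arm and unblinded (section 6.1.1), so no control group would show the shift.

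Section 5.3 lists ease of use, comfort and pain reduction among the performance claims, and section 7.1 expects the pilot to supply effect estimates for a full-scale study. A selected estimate would carry into both.

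**Working it through.** **1. Do the rules connect?** Section 4.3 stops the device. Section 15.4, as worded, is not limited to serious events and takes the subject out of the study. Section 6.3.6 can fill the place. The Day 21 rating requires a demonstration with the device, which an excluded subject has no stated route to give. If 15.4 is read as serious events only, the exclusion step falls away for irritation or pain. A subject who has stopped may then still lack an on-device Day 21 rating, any drop-out can still be replaced, and section 7 still has no rule for the gap.

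**2. The plan's own figure.** Section 7.2 gives a margin of error of 0.18 for n = 23, with no unit, confidence level, SD or proportion.
- As a proportion, z × √(p(1 − p)/23) at 95% is 0.204 for p = 0.5, 0.187 for p = 0.7 and 0.177 for p = 0.75. At 90% with p = 0.5 it is 0.171.
- As scale points, it needs an SD of 0.18 × √23 / 1.96 = 0.44, which is implausibly small on a 10-point scale.

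The figure can be reached only with an unstated input, so it is not used as a benchmark below.

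**3. Overstatement of the mean change.** Inputs: N = 23 (sections 6.3.9 and 7.2); k = subjects lost (assumed; six is the all-cause drop-out number in section 7.4); g = how many points worse the lost subjects' change is than that of those who stay (assumed).
- Without replacement, the mean over all 23 is the stayers' mean minus k × g / 23.
- With replacement, 23 + k are enrolled and 23 rated, so the overstatement is k × g / (23 + k). This assumes that replacements respond like the stayers.

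| k | g = 1 | g = 2 | g = 5 |
|---|---|---|---|
| 1, not replaced (÷ 23) | 0.04 | 0.09 | 0.22 |
| 1, replaced (÷ 24) | 0.04 | 0.08 | 0.21 |
| 3, not replaced (÷ 23) | 0.13 | 0.26 | 0.65 |
| 3, replaced (÷ 26) | 0.12 | 0.23 | 0.58 |
| 6, not replaced (÷ 23) | 0.26 | 0.52 | 1.30 |
| 6, replaced (÷ 29) | 0.21 | 0.41 | 1.03 |

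Replacement slightly lowers the overstatement. Points are on the 10-point scale of section 6.1.4. The Clinical Investigation Summary gives a 5-point scale for comfort, on which gaps in points would be smaller.

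**4. As a proportion improved (illustration).** Suppose 14 of 23 enrolled improve and none of the lost do. All enrolled: 14/23 = 60.9%. With 3 lost: 14/20 = 70.0%. With 6 lost: 14/17 = 82.4%.

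**5. As a test (illustration; the plan names no test).** With no true effect, n = 23 and a paired t-test at an assumed two-sided 0.05, the nominal chance of a significant result favouring the device is 2.5%. In 40,000 simulated studies without replacement:
- removing the worst 3 raises it to 24%, and the worst 6 to 59%;
- if removal correlates only 0.5 with the change, the figures are 8% and 14%;
- if it correlates 0.3, they are 5% and 7%.

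**The case against.** **The exclusion line may mean serious events only.** It sits in the section on serious adverse events, and other text separates stopping from leaving. Section 4.3 sends the subject to the nurse for instruction. Section 6.3.4 suspends garment use for pyrexia or infection and lists no mandatory removal for an adverse event. This stands. A reader might infer that irritation or pain always leads to exclusion; the documents do not say so. The wording leaves it open, and that itself needs correcting.

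**Replacement does not create the bias.** This also stands. It dilutes the bias slightly and needs approval. Its harm is that a full count of 23 can hide the losses.

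**Irritation need not make a dressing change difficult.** Fair: the route to ease of use is weaker than the route to comfort and pain.

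**The risk is small and this is a pilot.** Section 4.1.1 rates garment skin irritation 1 of 5 for likelihood, section 4.3 calls the possibility slight, and section 15.6 captures all adverse events. This limits the likely number lost and protects safety reporting. It does not protect the performance ratings, and with 23 subjects a few losses count.

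**Discomfort short of an adverse effect.** A reader might see a conflict between section 4.1.1 ("In the case of any discomfort the subject is requested to remove the wound care product") and section 2.4 ("If any unexpected discomfort or wound irritation occurs, please consult your doctor or nurse"). The two are compatible with each other and with section 4.3. Daily check-ins with a comments field, calls on Days 7 and 14 and continuous adverse-event recording largely cover the matter, so section 4.1.1 needs no edit.

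**Conclusion.** The point holds as a possibility written into the rules. Subjects who tolerate the garment badly can drop out of the Day 21 versus Day 0 comparison, and nothing secures or substitutes their rating. The direction favours the device, most plausibly for comfort and pain and possibly for ease of use.

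The size is unknown, because the documents give no stopping or exclusion rate and no SD. It is zero if every such subject still gives a Day 21 rating. The range of 0.04 to 1.30 points rests on assumed losses and gaps, and its top end is extreme because it assigns the whole all-cause drop-out number to intolerance.

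A reader might set these shifts against the 0.18 margin and conclude that one or two lost subjects would use it up. The documents do not support that: the unit of 0.18 is not stated, and reading it as scale points implies an SD of about 0.44.

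**What to change.** 1. In section 15.4, supply the missing noun and state which events lead to exclusion. Do not exclude subjects from follow-up or analysis for non-serious adverse effects.
2. When the device is stopped, take the short ease-of-use, comfort and pain rating, and keep the Day 21 contact for that subject.
3. Report the numbers stopped, excluded and replaced beside the Day 21 versus Day 0 results.
4. Add a sensitivity analysis of all enrolled subjects, including those replaced. Where Day 21 is missing, use the stopping rating, or else the last Day 7 or Day 14 on-device rating. Count subjects with neither as not improved, or show them as missing.

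**Cost.** One wording change, one short rating per subject who stops, one Day 21 contact for each, a line of counts and one extra analysis. The Day 7 and Day 14 ratings are already scheduled.

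**Limit.** The substitutes are early or unsupervised home ratings, not the observed Day 21 demonstration, and a Day 21 contact cannot by itself give an on-device rating from someone who has stopped. The analysis should therefore stay a sensitivity analysis.
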